8.1 Definition of Baseline

For safety evaluations, the Baseline assessment for all measurements will be the latest available, valid measurement taken prior to the initiation study medication, except for electrocardiography (ECG) values: The Baseline assessment for ECG include a triplicate assessment with the baseline value intended to be the arithmetic mean of the values taken at the Baseline assessment that are taken in triplicate. Baseline values for efficacy outcomes will be the average of screening and baseline visits where available. For the GST, the z-scores at each visit will be calculated using the mean over all patients of the average of screening and baseline, and using the standard deviation pooled across screening and baseline.

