- c Subject begins taking study medication in the clinic as soon as baseline procedures are completed, and eligibility confirmed. Date of first dose is noted as Day 1.
- d Where assent is in accordance with local laws, regulations and ethics committee policy.
- e Vitals and ECG will be measured in triplicate at Baseline and as single values at all other times. An average of the three measurements for ECG and blood pressure will be used for eligibility determination.
- f ECG at Screening visit repeated if QTc > 470 msec.
- g Neuropsychological assessments are not to be performed with fasted participant; ensure participant has been fed and meets blood glucose measurement requirements prior to any neuropsychological assessments.
- h Neuropsychological assessments are performed at the Early Termination Visit only when the visit is within 30 days of the last dose of study drug.
- i C-SSRS is administered to subject jointly with caregiver.
- j Blood Chemistry sample is collected in a fasted state (8-hour fast).
- k Provide a low carbohydrate/high protein meal or snack *after* fasting blood samples are drawn and *before* any neuropsychological assessments are performed.
- l Blood glucose measurement is an in-office point of care measurement after an appropriate period following the meal/snack, and prior to neuropsychological assessments are performed.
- m CT scan may be utilized for subjects with contraindication to MRI. MRI or CT should be done at least 14 days prior to the baseline visit to allow time for MRI report to support eligibility decision.

Table 2. Part 2 Schedule of Activities

Protocol Activity	Screening	Baseline	Treatment Period ^a										Follow-up ^b
	Day -60 to Day -1	Day -7 to Day 1	Day 1 ^c	Month 1	Month 2	Month 3	Month 6	Month 9	Month 12	Month 15	Month 18 /ET	3 months after last dose	
Study Days	-60 to -1	-7 to 1	1	30	60	90	180	270	360	450	540 or ET	630	
Window				±7d	±7d	±7d	±7d	±7d	±7d	±7d	±7d	±7d	
Sign informed consent / provide assent ^d	X												
Assessment of continued consent/assent		X					X	X	X	X	X	X	
Assign Screening ID	X												
Randomization			X										
Demographic information	X												
Review Inclusion/Exclusion Criteria	X	X	X										
Medical History / Surgical History / Drug, Alcohol, Tobacco Use History	X												
Complete Neuro Exam & Physical Exam	X												
Height	X												
ApoE genotyping		X											
Telephone contact				X	X								
Body weight	X	X				X	X	X	X	X	X	X	
BMI calculation	X												

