7.1.2 Vital Signs

Vital signs measurements will consist of blood pressure and pulse rate while the participant is supine. Vital signs will be conducted at all the study visits. Participant should have been supine at least 5 minutes prior to vital signs determination. At Baseline, pre-dose measurements will be performed in triplicate; all other vital signs readings (at time points shown in the Schedule of Activities) will be a single measurement. The baseline triplicate readings for blood pressure will be averaged for eligibility determination.

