5.2.3 Vital Signs

Vital signs measurements consist of blood pressure and pulse rate. Variables of analysis will include means, mean changes over time, and proportions of subjects meeting criteria for potential clinical concern in vital signs:

- Mean and mean changes in systolic and diastolic blood pressures
- Mean and mean changes in pulse
- Proportions of subjects with treatment-emergent values or changes of potential clinical concern.

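### Blood pressure and pulse are taken in triplicate at Baseline, but SAP 8.1 averages the triplicate for ECG only, so vital-sign changes are somewhat noisier than they need to be

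*SAP*

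**What the plan says.** Protocol 7.1.2 defines the measurements: "Vital signs measurements will consist of blood pressure and pulse rate while the participant is supine". It then sets how many are taken: "At Baseline, pre-dose measurements will be performed in triplicate". Footnote e to the schedule of activities puts vital signs and ECG under one rule: "Vitals and ECG will be measured in triplicate at Baseline and as single values at all other times". The SAP repeats this footnote in its own schedule (Section 13).

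The protocol gives the blood pressure triplicate one stated use: "The baseline triplicate readings for blood pressure will be averaged for eligibility determination". It states no use for the three pulse readings.

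SAP 8.1 defines the safety baseline: "the Baseline assessment for all measurements will be the latest available, valid measurement taken prior to the initiation study medication". The sentence continues with its one exception: "except for electrocardiography (ECG) values: The Baseline assessment for ECG include a triplicate assessment with the baseline value intended to be the arithmetic mean".

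SAP 5.2.3 lists the analyses that depend on this definition: "Mean and mean changes in systolic and diastolic blood pressures" and "Mean and mean changes in pulse". SAP 6.9.2 adds by-visit descriptive statistics for change from Baseline and rules out formal inference on vital signs. Neither section gives a different baseline for blood pressure or pulse, and nor does protocol 9.8.

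**The concern.** The schedule treats vital signs and ECG alike at Baseline, and the SAP's baseline definition does not. A programmer following SAP 8.1 literally would average three ECGs, but would take the last of three blood pressures and the last of three pulse readings.

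Two things follow. First, one Baseline visit can yield two blood pressures for the same subject: the mean used for eligibility and the last reading used for analysis. Second, the error of a single reading enters every change from Baseline in full, although two further readings that would dilute it are already in hand. Vital signs are a named safety endpoint, and Part 1 enrolled 43 subjects (SAP 1.4), so avoidable noise in these summaries is worth removing when that costs nothing.

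**Working it through.** The plan states no figure that depends on the vital-sign baseline, so there is none to reproduce. The check is a variance-components calculation.

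**Inputs from the documents**
- Readings at Baseline: 3. Readings at each later visit: 1 (protocol 7.1.2; schedule footnote e).
- Analysis baseline as written: one reading, the latest valid one before dosing (SAP 8.1).
- Quantity analysed: change from Baseline (SAP 5.2.3 and 6.9.2).

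**Assumptions**
- Reading = subject level + visit effect (variance V) + within-visit reading error (variance W).
- Visit effects are independent between visits. Reading errors are independent of each other, with a common mean within a visit.
- f = W/(V + W) is the within-visit share of the variance. The documents do not give it, so it is varied from 0.10 to 1.

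**Formulas.** The subject level cancels in a change.
- Baseline = last reading: Var(change) = (V + W) + (V + W) = 2V + 2W.
- Baseline = mean of three: Var(change) = (V + W) + (V + W/3) = 2V + (4/3)W.
- With V + W = 1 these are 2 and 2 − (2/3)f. The SD ratio, last reading to mean of three, is √[2 / (2 − (2/3)f)] = 1/√(1 − f/3).

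**Results**

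| f | Var, last reading | Var, mean of three | Excess variance | Excess SD |
|---|---|---|---|---|
| 0.10 | 2.000 | 1.933 | 3.4% | 1.7% |
| 0.25 | 2.000 | 1.833 | 9.1% | 4.4% |
| 0.50 | 2.000 | 1.667 | 20.0% | 9.5% |
| 0.75 | 2.000 | 1.500 | 33.3% | 15.5% |
| 1.00 | 2.000 | 1.333 | 50.0% | 22.5% |

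A simulation of 400,000 subjects at f = 0.50 gave variances of 1.995 and 1.663, against 2.000 and 1.667 from the formulas.

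The last row is a ceiling. It requires V = 0, meaning that blood pressure and pulse do not vary from visit to visit over six months apart from reading error. Under this model the direction is the same for any W above zero.

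**The case against.** The best textual defence is that SAP 8.1 does not say single or third reading. Its rule could be there to prefer the Baseline visit over Screening, with the whole triplicate counting as one measurement. The wording leaves room for this, but the structure of the paragraph argues against it: if a triplicate already counted as one measurement to be averaged, ECG would need no exception. Even on this reading, 8.1 does not say how three values become one, so a sentence is still needed.

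It is also fair to say that an analysis baseline may legitimately differ from an eligibility value, and that comparing one reading with one reading is a usable descriptive convention. That stands. The point is a free gain in precision and clarity, and the plan is not invalid without it.

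A reader might infer more than the documents support in three ways.

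- **False threshold crossings.** SAP 5.2.3 mentions proportions with values or changes of potential clinical concern, so baseline noise might seem to generate spurious cases. But the criteria tables in SAP Section 11 and protocol Appendix 1 cover only hematology and chemistry. With no blood pressure or pulse cut-off given, this cannot be shown or sized.
- **An apparent rise from downward drift.** If successive readings in one sitting fell, a last-reading baseline would look low against a lone later reading. Nothing in the documents establishes such drift. With a fall of d per reading, the third lies 2d below the first and the mean of three lies d below it, so averaging would halve the artefact without removing it.
- **A one-third cut in the noise.** Averaging lowers the reading-error variance of a change from 2W to (4/3)W, which is 33%. That is not the reduction in the variance of the reported change, which also carries 2V.

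**Conclusion.** The point holds as a minor one. As written, SAP 8.1 takes the last blood pressure and pulse reading as baseline and leaves the rest of the triplicate out of the change analysis, while ECG, collected under the same rule, is averaged. The cost is an SD of change about 2% to 10% larger than it would be with the mean of three, for an assumed within-visit share of 10% to 50%, and never more than 22.5% larger. These figures rest on independent readings with a common mean within a visit.

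The consequence is small. Vital signs are summarised descriptively, summaries of post-baseline values on their own are unaffected, and no efficacy test is involved. The same rule applies to both arms, so the documents give no ground for inferring a biased comparison between them.

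**What to change.** In SAP 8.1, extend the ECG exception to vital signs: Baseline systolic pressure, diastolic pressure and pulse are each the arithmetic mean of the triplicate readings taken at the Baseline visit before dosing. The latest valid pre-dose reading is used only where no triplicate is available. For blood pressure this also makes the analysis baseline the same average that is used for eligibility.

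The cost is one sentence and a small programming change. The readings are already collected, so there is no added burden on subjects or sites. It is best made before unblinding, so that the choice is plainly independent of the results.

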8.2 Missing Data

In general, missing clinical data will not be imputed, except where explicitly defined. In the event of study withdrawal, a subject's final assessment will be used as the endpoint value, if applicable.

Data are considered to be "on-treatment" if the assessment or collection follows the first administration of study medication and if the assessment occurs within 45 days following the final administration of study medication, justified based on the long half-life of this drug.

Dates with missing fields will not have days imputed.

In accordance with the recommendations of the report from the National Academy of Science (NAS) panel "*The Prevention and Treatment of Missing Data in Clinical Trials*," (National Research Council, 2010), sensitivity analyses will be done to ensure that study conclusions are robust against missing data. Last observation carried forward (LOCF) and baseline observation carried forward (BOCF) methods will be used as appropriate in sensitivity analysis. Missing data types will be examined, and statistical methodologies for appropriate sensitivity analyses will be finalized during blind data review as patterns emerge as the study progresses. Primary methodologies following the ITT principle are not subject to change.

The three types of missing data (Rubin, 1976) are considered to examine robustness of analysis conclusions against missingness and type of missingness:

- MCAR (missing completely at random) assumes the event of missingness is independent both of observable values and of unobservable values, and the missingness is entirely at random.
- MAR (missing at random) assumes that the missingness can be fully accommodated by accounting for variables where data are available.
- MNAR (missing not at random) the missingness may be related to the reason the data are missing.

The robustness of analysis conclusions against missingness is managed through supportive and sensitivity analyses, employing techniques MAR MI for placebo and MAR MI with delta adjustment (jump-to-placebo) for the group randomized to TTP488 (O’Kelly and Ratitch, *Clinical Trials with Missing Data: A Guide for Practitioners*, 2014).

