Further examination of the data showed clear differences in rate of placebo decline in ADAS-cog between the STEADFAST study (3 points in 18 months), the azeliragon Phase 2b study (10 points in 18 months) and that published for other similar studies (6 points in 18 months [Thomas 2016]), which may explain the lack of detectable effect in the STEADFAST study (the study was powered to detect a 4 point difference in change from baseline between active and placebo at 18 months, assuming a placebo decline of approximately 6 points over 18 months). It is hypothesized that subjects with higher expression of RAGE would present more inflammation and neurodegeneration and decline at a faster rate.

It has been demonstrated that advanced glycation endproducts accumulate in tissues of patients with diabetes with expression of RAGE increasing in response to injury and increases in ligand concentrations, including AGEs. This interaction of AGEs, and other ligands of RAGE, leads to sustained cellular damage and inflammation thus contributing to complications of diabetes including retinopathy, neuropathy and nephropathy. Further it has been shown that accumulation of AGEs parallels the development of cognitive impairment and dementia in patients with diabetes. Thus, patients with diabetes represent a sub-group expected to have increased concentration of RAGE ligands, increased expression of the RAGE receptor, have the potential to decline at a more rapid rate and thereby likely to respond to an antagonist of RAGE.

A comparison of placebo-treated subjects in the diabetic subgroup (defined as HbA1c \geq 6.5%) and the non-diabetic (HbA1c < 6.5%) complement of the target analysis set (subjects with evidence of cognitive impairment at Baseline [ADAScog \geq 10]) is provided in [Figure 1](#). Interestingly, the data show a clear difference in the rate of cognitive decline between the placebo subjects with diabetes and the placebo subjects without diabetes. The diabetic, placebo-treated subjects had numerically greater decline from baseline in the ADAS-cog when compared with the non-diabetic, placebo treated subjects. These data further support the hypothesis that subjects with presumed higher expression of RAGE present more inflammation and neurodegeneration and decline at a faster rate.

Figure 1. Change from Baseline in ADAS-cog: Comparison of Placebo-treated patients with HbA1c at Baseline $\geq 6.5\%$ and HbA1c $< 6.5\%$ (TTP488-301 A-Study [Target Analysis Set])

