9.7.2 Statistical Methodology for Primary Analysis

The primary analysis will use the ITT methodology and a main-effects mixed-models for repeated measures (MMRM) methodology. The MMRM will utilize an unstructured covariance where the number of parameters is “ $t(t+1)/2$ ” where “ t ” is the dimension of the covariance matrix, using PROC MIXED in SAS. In the unlikely event of lack of convergence, Toeplitz structure will be employed where the number of parameters is “ t ” where “ t ” is the dimension of the covariance matrix. Time is considered as a class variable. Analysis will include treatment, time and treatment-by-time interaction as fixed effects, Baseline as covariate, and subject as a random effect. Supportive modeling will also include MMRM main-effects model with treatment, time, and subject.

Model assumptions will be evaluated. If the parametric assumptions are evaluated as inappropriate or violated, rank analogues will be advanced.

The primary analysis will be done for each stage separately. Part 1 will use alpha = 0.0499, which includes an adjustment of 0.0001 for interim analyses performed by the Independent Data Monitoring Committee (IDMC). The alpha adjustment for the IDMC for Part 1 is considered to be negligible, hence, the stated alpha for Part 1 is 0.05 for the 100-patient, 6-month trial. Part 2 will use alpha = 0.049, which includes an adjustment of 0.001 for interim analyses performed by the Independent Data Monitoring Committee (IDMC), thereby preserving the overall study-wise alpha = 0.05. The alpha adjustment of 0.001 is considered to be appropriate for the 200-patient, 18-month study.

Multiple imputations (MI) will be used as a supportive analysis with 100 invocations (acknowledging that more invocations are needed with more missing data). Monte Carlo methods are planned.

An essential component of the thorough analysis includes an assessment of the impact of missing data on study conclusions. As a part of assessing this impact, supportive analysis will include:

- an endpoint analysis (reduction to last-observation-carried-forward, justified in this study based on the monotonic progression of the natural course of AD and assuming no more dropouts in the group treated with azeliragon than in the group treated with placebo)
- a completers analysis (observed cases at endpoint)
- observed cases by assessment time.

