1.4 Randomization

A total of 100 subjects were originally planned to be randomized into Part 1 of this study, but the total enrolled was 43 due to a slow enrollment and sponsor decision to stop enrollment due to the additive impact of the COVID pandemic on enrollment rates. Subjects were enrolled and randomized according to a fixed randomization scheme blocked by study investigative site.

Randomization is intended to have balanced allocation (1:1) between active and placebo. Dropouts will not be replaced.

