1.6 Sample Size and Power Considerations

Original Sample size considerations for Part 1 (from protocol):

Assuming a standard deviation of the change from Baseline to Month 6 in ADAS-cog14 of 4, using $\alpha = 0.05$, a total sample size of approximately 82 subjects in balanced allocation (41 subjects per group) provides at least 90% power to detect a difference between treatment groups of 2.9 using a 2-sided, 2-sample t-test. Assuming a dropout rate of 18% or less, randomization of 100 subjects provides adequate statistical power for Part 1 to demonstrate superiority of azeliragon over placebo based on the ADAS-cog14. (Section 9.2).

Recalculated power considerations for Part 1:

ADAS-Cog: Estimates and standard deviations were drawn from a model that fit change in ADAS-Cog11 over time using the data from the STEADFAST A-study and B-study combined (N=880). The model utilized all individuals in the study. Estimates were drawn at an HbA1C of 7.2 (average from present TTP488-305 study; Part 1). The estimates of standard deviation and effect size for the change from baseline in ADAS-Cog was 3.4 and -1.54 respectively. Given a sample size of 43, a two-sided α of 0.05 would result in 30% power to detect a significant effect. If we observe the estimated effect size and standard deviation at the given sample size in Part 1 of the current study (TTP-305) we would expect to observe a p-value of 0.144 which could be considered evidence of a trend.

Previous studies (Siemers et al 2016) suggest that mean to standard deviation ratio between ADAS-Cog 11 and 14 are similar, therefore it is expected that the estimates drawn using ADAS-Cog11 will be applicable to ADAS-Cog14 data.

Cognitive Composite: The association of treatment was also tested using a composite that was derived from STEADFAST A and B studies. Composites allow the global assessment of multiple aspects of disease as well as exclusion of items that do not contribute to progression and thus add noise to the data. The composite is composed of the ADAS-Cog comprehension, word finding difficulty, and remembering test instructions variables. The composite will be calculated by summing the within visit z-scores for each item across individuals. Z-scores are calculated by subtracting the individual item score at visit x from the baseline mean item score and dividing this value by the item standard deviation at baseline.

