* ADAS-Cog will also be run using LZCF. If neither of these are significant, the cognitive composites and global statistical test (GST) will be assessed for significance to demonstrate proof of concept. It is acknowledged that the present study is underpowered to replicate the clinically meaningful effect size observed in the STEADFAST combined A- and B-study diabetes subgroup. Therefore, if the observed effect size (treatment difference) or percent slowing (treatment difference divided by the placebo change) is equal to or greater than the corresponding values from the STEADFAST pooled analysis (-0.92; -61%), this will be considered proof of concept. Lack of strict statistical significance is expected with this range of effect size due to the small n, but this result, in the context of the consistency of the effect seen in STEADFAST Part A with the STEADFAST Part B data would provide proof of concept for this compound.

§ All secondary variables will also be run using LZCF.

3 Estimand Specification

This SAP is constructed to conform to regulatory guidance. In particular, this section is included as recommended by ICH E9 (R1) Addendum on estimands and sensitivity analysis in clinical trials to the guideline on statistical principles for clinical trials (30 August 2017).

In accordance with ICH E9 Addendum, the specification of the estimand is included in this SAP with the 4 attributes detailed in ICH E9 Addendum, Section A.3.1:

- A. The Population, that is, the subjects targeted by the scientific question:
For this study, the population consists of subjects with AD and HbA1c of 6.5% - 9.5% who meet eligibility requirements for the study, receive double-blind medication, and have at least one valid post-baseline measure of ADAS-cog(14).
- B. The variable (or endpoint) to be obtained for each patient, that is required to address the scientific question:
For this study, the primary endpoint is Change in ADAS-cog(14).
- C. The specification of how to account for intercurrent events to reflect the scientific question of interest:
Due to the small sample size intercurrent events will not be accounted for in this analysis.
- D. The population-level summary for the variable that provides, as required, a basis for a comparison between treatment conditions:
For this study, the population-level summary for the variable is the least-squares mean (LSM) of the treatment difference in mean change from baseline in ADAS-cog(14).

4 Populations of Analysis

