5.1.5 Efficacy Scales

Generation of instrument total scores will be calculated from individual items. The following instruments that are used in this study are subject to statistical analysis:

5.1.5.1 Alzheimer's Disease Assessment Scale - Cognitive Subscale 90 point (ADAS-cog):

- Range: The scale range is 0 to 90 with higher scores indicating greater cognitive impairment.
- Brief description: The 14-Item Alzheimer's Disease Assessment Scale - Cognitive Subscale (ADAS-cog14) is a structured scale (approximately 45 minutes to complete) that evaluates memory, orientation, attention, reasoning, language, constructional praxis, delayed recall, digit cancellation, and maze-completion. The ADAS-cog14 scoring range is from 0 to 90, with higher scores indicating greater cognitive impairment (Mohs et al. 1997). The ADAS-Cog should always be administered prior to other cognitive measures. The ADAS-Cog will be administered at Screening, Baseline, Months 3 and 6 or in the event of early termination. Participants must have scores of ≥ 10 at Screening and Baseline to be eligible for participation in the study.

5.1.5.2 Mini Mental State Examination (MMSE):

- Range: The scale range is 0 to 30 with lower scores indicating greater cognitive impairment.
- Brief description: The MMSE is a brief 30-point test that is used to assess cognition (Folstein, 1975). It is commonly used to screen for dementia. In the time span of about 10 minutes, it samples various functions, including arithmetic, memory and orientation. The MMSE will be administered at Screening, Baseline, Months 3 and 6 or in the event of early termination. Participants must have scores of 21-26 at Screening and 19-27 at Baseline to be eligible for participation in the study.

5.1.5.3 Functional Activities Questionnaire (FAQ):

- Range: The score ranges from 0 to 30. Higher scores are associated with greater impairment.
- Brief description: The FAQ is an inventory of instrumental activities of daily living developed by (Pfeffer 1982). The FAQ is administered by asking the informant to rate patient's ability (0-3) on 10 different activities of daily living. The FAQ will be administered at Screening, Baseline, Months 3 and 6 or in the event of early termination.

5.1.5.4 Amsterdam-Instrumental Activities of Daily Living Questionnaire (A-IADL):

- Range: scoring range from 20 to 80, with lower scores indicating greater impairment.

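### BOCF, named as a missing-data sensitivity analysis, flatters whichever arm loses more patients, because it gives dropouts zero decline in a worsening disease

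*SAP*

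**What the plan says.** SAP 8.2 and Protocol 9.12 carry the same sentence: LOCF and "baseline observation carried forward (BOCF) methods will be used as appropriate in sensitivity analysis". The stated purpose in both places is to show that conclusions are robust to missing data. The exact set of sensitivity methods is left to the blind data review.

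Three other parts of the plan bear on it.

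- **Direction and course.** SAP 5.1.5: "The ADAS-cog14 scoring range is from 0 to 90, with higher scores indicating greater cognitive impairment". Protocol 9.7.2 defends LOCF as "justified in this study based on the monotonic progression of the natural course of AD". Protocol 1.1.3 sets out how fast placebo patients worsened in the sponsor's own trials: "STEADFAST study (3 points in 18 months), the azeliragon Phase 2b study (10 points in 18 months"). It also cites a literature figure of 6 points over the same period.
- **Condition on LOCF.** Protocol 9.7.2 calls LOCF conservative only on the premise that azeliragon does not lose more patients than placebo. Neither document attaches a condition to BOCF.
- **Other missing-data methods.** SAP 8.2 also names multiple imputation under MAR for placebo, with a jump-to-placebo adjustment for azeliragon. SAP 6.6.2 adds multiple imputation and observed cases. In that imputation, a withdrawal for treatment failure has its endpoint value moved forward for progression. SAP 6.6 adds the last-z-score method.

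**The concern.** BOCF is usually offered as a severe test: a patient who leaves is denied any gain. That holds where the expected untreated course is to stay at, or return to, baseline. Here the expected untreated course is decline, so a carried-forward baseline credits the dropout with a better result than the average placebo completer. It also erases any worsening already recorded at an earlier visit, whereas SAP 6.6.2 projects treatment failures further along their decline.

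The check therefore rewards dropout. If azeliragon loses more patients, BOCF can show a benefit that does not exist. If placebo loses more, it can hide one that does. At stake is the claim that the result withstands missing data: an analysis that leans toward the arm with more dropout cannot support it.

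**Working it through.** **Inputs**

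- Part 1 size, SAP 1.4: "the total enrolled was 43 due to a slow enrollment". I take 22 vs 21 from the 1:1 allocation.
- Part 1 SD and effect, SAP 1.6: "The estimates of standard deviation and effect size for the change from baseline in ADAS-Cog was 3.4 and -1.54 respectively".
- Part 2 SD 7.5 and alpha 0.049, Protocol 9.2; 200 subjects, so 100 per arm, Protocol 3.0.
- Overall dropout 18% (Part 1) and 25% (Part 2), Protocol 9.2. No by-arm rates are given. I assume 23% vs 13% and 30% vs 20%, which average to those overall rates.
- Decline of 3, 6 or 10 points in 18 months, Protocol 1.1.3. If linear (assumed), 6-month decline is one third: 1.0, 2.0 and 3.33.

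**The plan's own figures.** The documents give no figure for BOCF, so I first reproduced the design figures that supply the inputs.

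- Part 1 as enrolled: SE = 3.4 × √(1/22 + 1/21) = 1.04; 1.54/1.04 = 1.48, so p = 0.145 (SAP: 0.144). Power by noncentral t is 30.5% (SAP: 30%).
- Part 2: 60 per group, SD 7.5, difference 4.5, alpha 0.049 gives 90.2% power (Protocol: at least 90%). 120/(1 − 0.25) = 160.

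These agree.

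**Bias formula.** Let μ be the placebo mean change, δ the true drug effect, and dA and dP the dropout proportions. If dropout is unrelated to outcome and dropouts are set to 0:

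BOCF difference = (1 − dA)(μ + δ) − (1 − dP)μ = (1 − dA)δ − (dA − dP)μ

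- No drug effect: −(dA − dP)μ. A negative value favours azeliragon.
- Equal dropout: (1 − d)δ, which is dilution only. At 18%, −1.54 becomes 0.82 × (−1.54) = −1.26. At 25%, 4.5 becomes 0.75 × 4.5 = 3.4.
- Splits reversed: the same bias, favouring placebo.

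**Size with no drug effect.** The bias comes from the formula. The rates come from simulation: completers normal, dropout counts random, dropouts set to 0, two-sample t-test at two-sided alpha 0.0499 (Part 1) or 0.049 (Part 2). I counted significant results favouring azeliragon; the nominal rate is about 2.5%.

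| Setting | Dropout, azeliragon vs placebo | Decline μ | Bias | Favourable false-positive rate |
|---|---|---|---|---|
| Part 1, N = 43 | 23% vs 13% | 1.0 | −0.10 | 3.3% |
| Part 1, N = 43 | 23% vs 13% | 2.0 | −0.20 | 4.1% |
| Part 1, N = 43 | 23% vs 13% | 3.33 | −0.33 | 5.3% |
| Part 2, 100 per arm | 30% vs 20% | 3 | −0.30 | about 5% |
| Part 2, 100 per arm | 30% vs 20% | 6 | −0.60 | about 9% |
| Part 2, 100 per arm | 30% vs 20% | 10 | −1.00 | about 14% |

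The largest Part 1 bias is 0.33/1.04, about a third of a standard error.

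**The case against.** The best defence has four parts.

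1. **No decision rests on BOCF.** It is absent from the primary model (SAP 6.2), the testing sequence and proof-of-concept rule (SAP Section 2) and the composite analyses. This stands. A reader might infer that the primary result, or a proof-of-concept declaration, is biased; the documents do not support that.
2. **It is optional, and the choice is made blind.** This helps less than it seems. Whether BOCF is harmless depends on dropout by arm, which a blinded review cannot see, so the balance condition that Protocol 9.7.2 places on LOCF could not be checked for BOCF at that point.
3. **Better methods are already planned.** True: jump-to-placebo imputation stands in the same section. That limits the harm and makes the repair easy, but it does not make BOCF a valid check beside it.
4. **The larger figures belong to Part 2.** Correct. This SAP covers Part 1 only, where the effect is modest. Part 2 is reached through Protocol 9.12, and Protocol 9.0 foresees a possible SAP update before Part 2 is unblinded.

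A reader might also connect this with the acute, reversible cognitive worsening mentioned in Protocol 1.1.4, and infer that BOCF would conceal drug-related harm. That passage ties the worsening to concentrations that doses above 5 mg/day might reach. The documents do not say it is expected at the study dose, and the point here does not need it.

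**Conclusion.** The point holds as a defect in one named sensitivity analysis. BOCF is biased toward the arm with more dropout, in either direction, and neither document attaches a safeguard. In Part 1 the bias is a few tenths of a point or less. In Part 2 it could reach about 1 point with a 10-point excess of dropout and the fastest decline the protocol quotes. It would be wrong to read this as a bias always in favour of azeliragon: equal dropout dilutes a real effect, and more placebo dropout works against the drug.

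The sizes rest on assumed by-arm dropout, linear decline to Month 6, dropout unrelated to outcome, and declines taken from earlier studies (STEADFAST used ADAS-cog11) rather than a planning value for ADAS-cog14. The zero is exact only on raw change with the SAP 8.1 averaged baseline carried forward; SAP 6.2 models a risk-adjusted change score, for which I have not computed the bias.

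**What to change.** Delete BOCF from SAP 8.2 and Protocol 9.12. Let the jump-to-placebo multiple imputation already named in SAP 8.2 serve as the stress test, and state in advance a range of delta shifts toward worse scores for azeliragon dropouts, so that the reader can see how large a shift would overturn the conclusion. Report dropout by arm beside it.

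The cost is wording in two sections and a few extra runs of an imputation already planned. No new data are needed.
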